## 6.0 Research Locations:

The evaluation will take place on site at The New England Consortium (TNEC) training center at Wannalancit Mills, as part of the University Massachusetts Lowell Campus. The facility is well equipped with the space necessary and standard equipment provided for training. The site is located at the heart of Lowell, offers shuttle bus service, state-of-the-art fiber optic cable and HVAC, and 7 elevators and 4 loading docks enabling easy access for trainees of any

background, disability status, or socioeconomic status, and has the ability to host and maintain a VR exercises for evaluation.

In addition to the Wannalancit Mills location, the evaluation will also take place at various offsite locations where TNEC has been contracted to deliver the 40-hour HAZWOPER training.

All required permissions and approvals are already obtained to conduct this research at TNEC.

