### **3.0 Inclusion and Exclusion Criteria:**

We will seek out participants who self-select to participate in the New England Consortium (TNEC) training offerings through open enrollment, including populations of any racial or ethnic background.

We will also seek out participants who are experienced trainers involved in delivering the New England Consortium (TNEC) training offerings, including trainers from any racial or ethnic background.

Participants must meet the eligibility requirements for the class. Given the class requires students to complete standardized HAZMAT training in fully suited PPE with a self-contained breathing apparatus, students must be able to speak and understand English, and not be pregnant.

The HAZWOPER certification course falls under TNEC's open enrollment courses. TNEC offers on an ongoing basis at their training center in Lowell, Massachusetts. The open enrollment courses generally consist of 15-25 students from various employers or organizations with a variety of backgrounds. Prior to each open enrollment course, TNEC trainers review the student enrollment's business types, chemical handling information and hazard exposures. Upon this review the trainers will personalize the course to best meet the needs of the attendees.

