## 4.0 Sample Size:

According to The New England Consortium, during the pandemic they have trained approximately 15-25 people per class once a month.

Our study follows two stages. First, we will conduct a Pilot consisting of 2 months with one month serving as a case and the other month serving as the control. The Pilot will be used to indicate effect size. (30-50 participants)

Our study will also include the main evaluation, consisting of 6 randomly selected courses that receive the IMPRINT VR intervention and 6 randomly selected control courses. (180-300 participants)

This creates a sample of approximately 300 participants.

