## 5.0 Recruitment and Screening Methods:

**Recruitment process:** Given participants opt into training we will use a convenience sampling frame. Recruitment will consist of including the term, “Virtual Reality Immersive Activities”, to the existing course title and course link. The current open enrollment advertisement is available through this link: <https://tnectraining.org/training/schedule-register/>

**Screening process:** N/A

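### Eligibility and recruitment describe open enrollment only, yet contracted offsite courses are also in the evaluation, and no stratification by setting is stated for the 12 courses

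*Combined protocol and SAP*

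**What the plan says.** **Who is eligible (Section 3.0).** The trial seeks people who "self-select to participate in the New England Consortium (TNEC) training offerings through open enrollment". The section adds that "The HAZWOPER certification course falls under TNEC's open enrollment courses" and places these at the Lowell training center. It describes the usual class: "The open enrollment courses generally consist of 15-25 students from various employers or organizations with a variety of backgrounds". Trainers look at who has enrolled and adapt the course: "Upon this review the trainers will personalize the course to best meet the needs of the attendees".

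**How they are recruited (Section 5.0).** A phrase about virtual reality is added to the existing course title and link. Only one source is cited: "The current open enrollment advertisement is available through this link".

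**Where the evaluation runs (Section 6.0).** It runs at the Lowell site and also at "various offsite locations where TNEC has been contracted to deliver the 40-hour HAZWOPER training". No other section mentions these contracted courses.

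**How courses reach an arm (Section 4.0).** The main evaluation has "6 randomly selected courses that receive the IMPRINT VR intervention and 6 randomly selected control courses". No selection method, stratification or balancing rule is given.

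**How the arms are compared (Section 8.0).** Before analysis of the 12-month study, intervention and control samples are matched by Euclidean distance. The matching uses trainee and trainer characteristics, including cohort characteristics and prior knowledge from registration. The arms are then compared by t-test. Setting is not named in either step, and the unit of the t-test is not stated.

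**The concern.** Two things are unsettled. The first is scope. As written, the eligibility and recruitment text does not reach trainees in contracted offsite courses, although Section 6.0 puts such courses in the evaluation. A reader cannot tell how those trainees enter the study or whether their courses are among the 12.

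The second is comparability. An offsite class meets in a different facility, and its members may have arrived by another route with a different mix of employers and experience. The stated objective in Section 1.0 is adherence during hands-on field exercises, which could plausibly depend on the site. With only six classes per arm, a few offsite courses landing in one arm would shift the difference between arms by an amount unrelated to VR. Nothing in the available text is designed to prevent or remove that.

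**Working it through.** **The plan's own figure first.** 12 courses × 15 = 180 and 12 × 25 = 300, which reproduces the 180-300 given for the main evaluation. The pilot's 2 courses give 30-50, also as stated. So there are 12 units of allocation, 6 per arm.

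**Inputs not in the documents (assumptions).** Number of offsite courses among the 12, *k*: 2, 3 or 4. Difference in mean outcome between settings: 0.3 SD, with 0.5 SD as a larger case. ICC 0.05, with 0.10 and 0.20 shown. 20 trainees per class, the middle of 15-25. Selection is unrestricted and classes are of equal size.

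**Step 1: chance that all offsite courses fall in one arm.** P = 2·C(12−k, 6)/C(12, 6), with C(12, 6) = 924.
- k = 2: 2 × 210/924 = 0.455
- k = 3: 2 × 84/924 = 0.182
- k = 4: 2 × 28/924 = 0.061

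**Step 2: shift in an unadjusted contrast.** Shift = setting difference × (difference in number of offsite courses)/6.

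**Step 3: class-level standard error.** SE = √[2 × (ICC + (1 − ICC)/20)/6]. At ICC 0.05 this is √[2 × (0.05 + 0.0475)/6] = √0.0325 = 0.18 SD. At ICC 0.10 it is √0.0483 = 0.22, and at 0.20 it is √0.08 = 0.28.

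| k | P(all in one arm) | Shift at 0.3 SD | Shift ÷ SE of 0.18 | Shift at 0.5 SD |
|---|---|---|---|---|
| 2 | 45% | 2/6 × 0.3 = 0.10 | 0.56 | 0.17 |
| 3 | 18% | 3/6 × 0.3 = 0.15 | 0.83 | 0.25 |
| 4 | 6% | 4/6 × 0.3 = 0.20 | 1.11 | 0.33 |

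The larger shifts go with the smaller probabilities. When k = 3 does not split 3-0 it splits 2-1, and the shift is 1/6 × 0.3 = 0.05 SD.

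**Step 4: less extreme imbalance.** The chance that the arms differ by two or more offsite courses is 45%, 18%, 55%, 24% and 57% for k = 2, 3, 4, 5 and 6. Allocation within setting would hold the difference to 0 for even k and 1 for odd k.

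**Step 5: how much of this the SE already contains.** With 3 of 12 courses offsite and a 0.3 SD difference, setting contributes 0.25 × 0.75 × 0.3² = 0.017 to the between-class variance, about a third of the assumed 0.05. Removing it leaves 0.033, and the SE becomes √[2 × (0.033 + 0.0475)/6] = 0.16 instead of 0.18. This ignores the small cost of the 2-1 split that k = 3 makes unavoidable.

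**The case against.** The strongest reply is that the courses are described as randomly selected. If they are, any imbalance in setting arises by chance and in either direction, and it is part of the between-class variance that a class-level SE measures. The shifts above are then not a bias to be added to that SE. This stands: the loss is precision, plus the risk of an unlucky allocation that the plan could have prevented.

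Second, the plan does have a control for class differences: matching on cohort characteristics and prior knowledge. Those are two of the routes by which setting might act, so part of its effect may be captured. But setting is not a named variable. If every offsite course falls in one arm, the other arm has no offsite course to match, and setting cannot be separated from arm.

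Third, much about the offsite courses is inferred. The documents do not say how contracted trainees register, that their classes have a different mix, or that field exercises are set up differently there. Section 8.0 does state the same workbook, content and assessment sequence across arms, although that speaks to arms and not to settings. Design details in the figures that are not shown cannot be checked.

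A reader might go further and infer that VR courses will be concentrated at Lowell, because Section 6.0 describes that site as able to host VR exercises and says nothing similar of offsite venues. That would make the confounding systematic. The text neither states nor excludes it, so it cannot be asserted.

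**Conclusion.** The scope mismatch between Sections 3.0 and 5.0 and Section 6.0 is real and needs correcting whatever the number of offsite courses. The statistical consequence is moderate and conditional. For 2 to 4 offsite courses, complete separation of setting by arm has probability 45% down to 6%. The accompanying shift is 0.10 to 0.20 SD if settings differ by 0.3 SD, or roughly 0.6 to 1.1 class-level standard errors. The number of offsite courses, the setting difference and the ICC are all assumptions. If none of the 12 is offsite, the comparability issue disappears.

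A reader might infer that such an imbalance would pass for a VR effect. The figures do not support that. In the k = 3 case the shift is 0.83 SE. Even against an individual-level t-test that ignored clustering (120 per arm, SE = √(2/120) = 0.13 SD) it is 0.15/0.129 = 1.16 SE. Neither reaches significance alone. The plan should be changed because allocation within setting is a better and inexpensive method with 12 units, not because bias has been shown.

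**What to change.** 1. Amend Sections 3.0 and 5.0 to cover contracted courses: who is eligible, how trainees are recruited, and how many such courses are expected. State whether these courses count toward the 12.
2. Randomise courses to arm separately within Lowell and offsite, using blocked lists, so that the arms differ by at most one offsite course. For odd k, link the two lists so that the split stays 6:6.
3. Include setting as a covariate in a class-level comparison, and name it in the analysis text.

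**Cost.** Protocol wording, a stratified allocation list and one degree of freedom (10 to 9 with 12 classes and two arms). The lists need a reasonable forecast of contracted courses.

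**Alternative.** Restrict the randomised comparison to Lowell open-enrollment courses. This matches Section 3.0 as it stands and removes the setting question, but it is a trade-off. Section 4.0 reports about one class a month, so 12 courses already fill the 12 months. If offsite courses are being counted on, restriction would lengthen the trial or reduce the number of classes.

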## **7.0 Multi-site Research (research that involves external collaborating institutions and individuals):**

N/A

## **8.0 Procedures Involved:**

The standard TNEC 40-hour workbook will be used in both the intervention and control classes.

In the intervention, trainees will be provided with an Oculus VR headset to complete virtual reality modules based on activities covered in the TNEC 40 hour course workbook. In control classes, trainees will complete all of the activities following standard practice which includes filling out sheets, reviewing 2D photographs, and reviewing slides. VR modules will last no longer than 1-5 minutes in length, which is a comparable length to the time allowed for students in control classes to complete their assigned tasks. There will be no differences in content provided between cases and controls. We are examining the effect of a difference in delivery mechanism and interaction with the content to enhance retention, understanding, and performance.

VR modules will be provided intermittently throughout the 40 hour course. Each course is required to be 40 hours in length by the OSHA standard.

All evaluations and assessments of trainees will take place at the same sequence between cases and controls.

Outcomes measured include student accuracy on the TNEC HAZWOPER performance instruments including; 1) the 40 Hr HazWoper Course Workbook, 2) the Toxic Properties Activity, 3) The New England Consortium Health and Safety Training Survey, 4) System Usability Scale (SUS), 5) Occupational Self-

Efficacy Scale - Short Form (OSS-6), 6) iGroup Presence Questionnaire (IPQ), 7) Flow State Scale (FSS), 8) UX for VR Questionnaire, and 9) NASA-TLX

We will first run a two-month pilot to estimate ICC, the intraclass correlation coefficient. We will use ICC to determine effect size for the following 12-month study (see Figure 10). Using this calculation, we will determine expected effect size from the more extensive 12-month portion of the evaluation effort.

Prior to analysis of the 12-month effort, we will use matching techniques based on trainee and trainer characteristics. We will use pretest matching criteria based on trainee cohort population characteristics and prior knowledge ascertained through pre-HAZWOPER training registration information.

[figure not shown]
[figure not shown]
We will match cases and controls using Euclidian distance between intervention and control samples rather than propensity score matching to find the best match to mitigate risk of confounding due to low sample size following the guidance of [name] (King, G. and Nielsen, R., 2019. Why propensity scores should not be used for matching. *Political Analysis*, 27(4), pp.435-454.). We will compare how these modules enhance student performance across TNEC HAZWOPER performance instruments including; 1) the 40 Hour HAZWOPER Course Workbook, 2) the Toxic Properties Activity, 3) The New England Consortium Health and Safety Training Survey, 4) System Usability Scale (SUS), 5) Occupational Self-Efficacy Scale - Short Form (OSS-6), 6) iGroup Presence Questionnaire (IPQ), 7) Flow State Scale (FSS), 8) UX for VR Questionnaire, and 9) NASA-TLX

We will compare how these modules enhance performance through a t-test.

[figure not shown]
Intervention VR modules will be based on the existing activities within the 40 Hour HAZWOPER Course Workbook and the field exercise including:

Module 1 Duration: 5 Minutes	Activity 3-A What's on the Site?
------------------------------------	----------------------------------

[figure not shown]
Instrument	
3.1 CHEMICAL HAZARDS - 3 • Pg 4
 
ACTIVITY3-A
 
WHAT'S ON THE SITE?
 
Purpose: To start developing a list of clues that can be used to decide if hazardous chemicals are present on site. To get you thinking about what you need to know in order to work safely on site. To stress the importance of information and knowing where to get it.
 
Task: As a group, answer questions 1-3 using the following information: the site description below, the site map on pg. 5, and the photographs in your site packet. Numbers on the site map correspond to photo numbers. The arrows indicate the direction from which the photo was taken.
 
Site Description: Bright Corporation was a small metal plating company located on a 2 acre site. It operated between 1955 and 1992. The company was engaged in plating and painting of small metal parts. A lead acid battery manufacturer occupied the site between 1992 and 1995. The site has been abandoned for six months.
 
 
1. What clues suggest that chemical hazards may be present?
 
2. What else would you like to know about this site before entering?
 
3. Where would you go for this information?
 

IMPRINT Intervention (Virtual Environment)	

[figure not shown]
Control Part A	
Control Part B	
Module 2 Duration 5 Minutes	Activity 11-A Controlling the Site

Instrument	
DANGER HAZARDOUS WASTE 3.1 Ch. 11 • Pg 13
 
ACTIVITY 11-A
 
CONTROLLING THE SITE
 
PURPOSE: To review the health & safety issues to be considered when developing a site control program.
 
TASK: You are in charge of buried drum removal at the Bright Corporation site. Contaminants include acids and bases, flammable solvents, chlorinated organic solvents, and metals. Using the site map on page 15 and the job description below, answer the questions on the next page.
 
 
• Drums are being unearthed manually using shovels.
 
• They are removed from the pit using an excavator with a drum grappler attached.
 
• Drums are then moved manually, using drum dollies, to the first staging area for opening and sampling.
 
• They are then moved to final staging area with dollies to await bulking and removal.
 
• Emptied drums are crushed before removal.
 
• The excavation has had problems with water build up. The water is pumped using a gasoline pump to a holding area for testing and later removal.
 
• Workers entering the excavation and workers in the drum opening area are in level B protection. Workers in sampling area in level C. All others in the exclusion zone are in level D protection.
 

IMPRINT Intervention (Virtual Environment)	

Control	 
ACTIVITY 11- A (continued)
 
DANGER HAZARDOUS WASTE
 
3.1 Ch. 11 • Pg 15
 
Site Plan Labels:
 
 
EXCAVATION
 
SPOILS PILE
 
EXCAVATOR w/ SPREADER
 
CHANLINK FENCE
 
EQUIPMENT DECON
 
DRUM CRUSHER
 
PERSONNEL DECON
 
SUPPORT ZONE TRAILER
 
RESERVOIR
 
PUMP
 
BUILDING
 
BUILDING
 
BUILDING
 
PREVAILING WIND
 
W-E
 
N
 
S
 
HOT ZONE
 
WARM ZONE
 
COLD ZONE
 

Module 3 Duration 3 Minutes	Decontamination Line Ordering and Field Exercise

Instrument (field training exercise/ evaluation)
		

IMPRINT Intervention (Virtual Environment)
		

Control	
Sample Decon - Level "A"
 
HOT LINE
 
EXCLUSION OR HOT ZONE
 
CONTAMINATION REDUCTION ZONE
 
WARM LINE
 
CLEAN ZONE
 
EQUIPMENT DROP
 
SAND BOX (for gross boot decon)
 
BOOT AND GLOVE RINSE
 
REMOVE CHICKEN BOOTS
 
REMOVE HEAVY OUTER GLOVES
 
WHOLE BODY WASH
 
WHOLE BODY RINSE Check for efficacy
 
REMOVE BOOTS
 
REMOVE SUIT
 
OFF AIR
 
REMOVE SCBA BACKPACK
 
REMOVE FACE MASK (Entrant does for him/herself)
 
REMOVE GLOVES (Entrant does for him/herself)
 
PERSONAL SHOWER
 
MEDICAL MONITORING
 
Module 4	Visual Inspection Checklist


Duration 5 Minutes
 
Instrument
	
Visual Inspection Checklist
 
 Note the types of containers, impoundments, or other storage systems:
 
 
- Paper or wood packages
 
- Metal or plastic barrels or drums
 
- Underground tanks
 
- Above ground tanks
 
- Compressed gas cylinders
 
- Pits, ponds, or lagoons
 
 
 Note any tags, labels, markings, or other identifying indicators.
 
 Note the condition of waste containers and storage systems:
 
 
- Sound (undamaged)
 
- Visibly rusted or corroded
 
- Leaking or bulging
 
- Size and type of container
 
- Labels on containers indicating corrosive, explosive, flammable, radioactive, or toxic materials
 
 
 Note the physical condition of the materials:
 
 
- Gas, liquid, or solid
 
- Color and turbidity
 
- Behavior, e.g., corroding, foaming, vaporizing, or crystallizing
 
- Conditions conducive to splash or contact
 
 
 Identify natural wind barriers:
 
 
- Buildings
 
- Fences
 
- Vegetation
 
 
 Determine the potential pathways of dispersion:
 
 Note any indicators of potential exposure to hazardous substances:
 
 
- Dead fish, animals or vegetation
 
- Dust or spray in the air
 
- Fissures or cracks in solid surfaces that expose deep waste layers.
 
- Pools of liquid
 
- Gas generation or effervescence.
 
- Deteriorating containers
 
- Cleared land areas or possible landfill areas
 
- Subsiding areas indicating waste burial locations
 
 
 Note any safety hazards. Consider:
 
 
- Conditions of site structures
 
- Obstacles to entry and exit
 
- Terrain homogeneity
 
- Terrain stability
 
- Stability of stacked material
 
 
 Identify any reactive, incompatible, flammable, or highly corrosive wastes.
 
 Note land features.
 
 Note the presence of any potential naturally occurring skin irritants or dermatitis-inducing agents, for example:
 
 
- Poison ivy
 
- Poison oak
 
- Poison sumac
 
 
 Collect samples:
 
 
- Air
 


IMPRINT Intervention (Virtual Environment)
	

Control
	

Module 5 Duration 5 Minutes
	
Chemical Properties

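### With one class per arm, the pilot cannot estimate the ICC or give a usable expected effect size, and the readable text gives no detectable difference for 6 v 6 classes

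*Combined protocol and SAP*

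**What the plan says.** Section 8.0 gives the pilot a statistical purpose: "We will first run a two-month pilot to estimate ICC, the intraclass correlation coefficient". It continues "We will use ICC to determine effect size for the following 12-month study (see Figure 10") and adds "Using this calculation, we will determine expected effect size from the more extensive 12-month portion of the evaluation effort". Section 4.0 gives the same pilot a second purpose: "The Pilot will be used to indicate effect size. (30-50 participants").

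Section 4.0 also fixes the pilot's size. The training centre has "trained approximately 15-25 people per class once a month", and the study begins with a "Pilot consisting of 2 months with one month serving as a case and the other month serving as the control". The main evaluation has "6 randomly selected courses that receive the IMPRINT VR intervention and 6 randomly selected control courses. (180-300 participants").

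Section 8.0 plans matching before the 12-month analysis ("We will use pretest matching criteria based on trainee cohort population characteristics and prior knowledge") and names a t-test as the comparison, without saying whether its unit is the trainee or the class. The readable text states no alpha, power, SD, ICC, target effect or detectable difference. Figure 10, cited where the effect-size calculation is described, is not shown.

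**The concern.** An ICC measures how far classes differ from one another compared with how far trainees differ within a class. Estimating it in a two-arm study needs at least two classes in some arm, and this pilot has one in each. Any difference between the two classes could come from VR, from the trainees who enrolled, from the trainer or from the month, and the data cannot separate these.

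The reasoning from ICC to effect size is also faulty. Together with class number, class size, alpha and power, an ICC determines the difference a trial can *detect*. It says nothing about the difference to *expect*.

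The stakes are limited. The documents tie no resizing or go/no-go decision to the pilot result, and the 6 v 6 layout is already set. What suffers is interpretation. A chance gap between two classes could be reported as the expected effect. Unless Figure 10 supplies it, a reader of a null result would not know what 12 classes could have detected.

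**Working it through.** **1. The plan's own counts (section 4.0).** Main evaluation: 12 x 15 = 180 and 12 x 25 = 300. Pilot: 2 x 15 = 30 and 2 x 25 = 50. Both stated ranges reproduce exactly, and the second confirms one class per arm.

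**2. Degrees of freedom.** Between-class df within arm = classes - arms. Pilot: 2 - 2 = 0. Main evaluation: 12 - 2 = 10. With 0 df no estimator can separate class variance from the VR effect. This step needs no assumed number.

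**3. Assumptions for sizes.** Not in the documents: ICC 0.01, 0.05, 0.10, 0.20 (results follow this order); total SD 1; equal class sizes; two-sided 0.05; 80% power; one unadjusted outcome. Class size m = 20 is the middle of the stated 15-25.

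**4. Pilot gap.** Variance of a class mean = ICC + (1 - ICC)/m = 0.0595, 0.0975, 0.145, 0.240.
- SE of the gap = sqrt(2 x variance) = 0.345, 0.442, 0.539, 0.693.
- With no true effect, P(|gap| > 0.5) = 2[1 - Phi(0.5/SE)] = 15%, 26%, 35%, 47%.
- 95% half-width if the ICC were known, 1.96 x SE = 0.68, 0.87, 1.06, 1.36 SD.

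**5. An ICC computed by ignoring arm.** This leaves 1 df, and a true effect d adds d²/2 to the apparent between-class variance (0.125 for d = 0.5). Simulation of the ANOVA estimator, two classes of 20, 200,000 draws:
- True ICC 0.05, no effect: 95% of estimates lie between -0.05 and 0.34, and 51% are negative.
- True ICC 0.01, effect 0.5 SD: the median estimate is 0.07.

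**6. Detectable difference, 6 v 6 class means.** SE = sqrt(2[ICC + (1 - ICC)/m]/6). The noncentral t on 10 df gives a multiplier of 3.11. Example, m = 20 and ICC 0.05: SE = sqrt(2 x 0.0975/6) = 0.180; 3.11 x 0.1803 = 0.561.

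| Trainees per class | ICC 0.01 | 0.05 | 0.10 | 0.20 |
|---|---|---|---|---|
| 10 (if matching drops trainees) | 0.593 | 0.684 | 0.783 | 0.950 |
| 15 | 0.495 | 0.604 | 0.718 | 0.904 |
| 20 | 0.438 | 0.561 | 0.684 | 0.880 |
| 25 | 0.400 | 0.533 | 0.662 | 0.865 |
| 20, six pairs, 5 df, no gain from matching | 0.495 | 0.633 | 0.773 | 0.994 |

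On 5 df the required difference is 1.130 times larger, so pairing breaks even when paired class means correlate at 1 - (1/1.130)² = 0.22.

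**7. Unit of the t-test.** If trainees were the unit (120 v 120), simulation gives false-positive rates of about 7%, 16%, 25% and 38%, against 5% for class means.

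**8. ICC from the main evaluation.** With 12 classes of 20, 10 df and true ICC 0.10, 95% of within-arm estimates lie between 0.00 and 0.22.

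**The case against.** - **Figure 10 may contain the calculation.** This stands: the absence of a detectable difference can be asserted only of the readable text. The figure cannot rescue the pilot, because an ICC from one class per arm would still be unidentifiable.
- **There may be more pilot classes.** Section 6.0 mentions contracted offsite courses. The 30-50 head count leaves no room for further classes of 15-25.
- **Effect size may loosely mean detectable effect,** for which an ICC is a proper input. That is a possible reading of one sentence, although section 8.0 also speaks of the expected effect size. Neither reading restores the missing degrees of freedom.
- **No decision hangs on the pilot.** This is true, and it limits the point to what the trial can claim.
- **Sensitivity could be better than shown.** This stands. Section 8.0 says prior knowledge will be obtained from registration information, and class means could be adjusted for it. With an assumed correlation of 0.5 between baseline and outcome class means (variance x 0.75, 9 df, 20 per class), the detectable differences become 0.38, 0.49, 0.60 and 0.77 SD.
- **The unit of the t-test is a separate matter.** It can be judged separately and adds no weight here. It is mentioned because a 6 v 6 detectable difference has no meaning until the unit is named.

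**Conclusion.** The concern holds and should be fixed. The pilot's stated purpose cannot be met. With 0 between-class df there is no within-arm ICC, and the VR-control gap is fully confounded with class and month. That conclusion rests on section 4.0 alone. The sizes rest on the assumed ICCs. They indicate that a pilot gap above half an SD would be common by chance, and that 6 v 6 classes could detect roughly 0.4 to 0.9 SD. Those detectable differences are illustrations and do not show that the trial is underpowered. The statement that none is given is conditional on Figure 10.

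**What to change.** 1. **Sections 4.0 and 8.0:** remove the use of the pilot to estimate the ICC or the effect size. Suggested wording: *The pilot (one VR class, one control class) tests feasibility and scoring and gives a within-class SD.*
2. **Section 8.0, analysis:** state that the t-test is on class means, or use a mixed model with a class effect and small-sample degrees of freedom.
3. **Section 4.0:** give the 6 v 6 detectable difference over a labelled range of ICCs, or reconcile it with Figure 10 if that already gives one. The 20-per-class row above can serve, with every assumption stated. Note what would worsen it (trainees dropped in matching, several outcomes sharing the 0.05, a paired analysis on 5 df) and what could improve it (adjustment for baseline knowledge).
4. **Main evaluation:** estimate the within-arm ICC from the 12 classes and report it with its interval.

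The cost is rewording, one short table and a named unit of analysis, with no extra classes or data. The stated sensitivity will look less favourable, and the ICC from 12 classes will be imprecise. Enlarging the pilot is a poor alternative: two classes per arm would take four months and give only 4 - 2 = 2 between-class df.
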